8.5.1.1. Criteria for the Calculation of Apparent Terminal Elimination Rate Constant and Half-Life

The start of the terminal elimination phase for each subject will be defined by visual inspection and generally will be the first point at which there is no systematic deviation from the log-linear decline in concentrations.

The apparent terminal elimination rate constant (λ_z) will only be calculated when a reliable estimate can be obtained using at least 3 data points, preferably not including C_{max} , and the adjusted coefficient for determination of exponential fit (R^2 -adj) of the regression line is ≥ 0.7 . Parameters requiring λ_z in their calculation (eg, AUC_{0-inf} , $t_{1/2}$, CL/F and V_z/F) will only be calculated if the R^2 -adj value of the regression line is ≥ 0.7 .

The following regression-related diagnostic PK parameters will be determined:

Parameter	Units	Definition
λ_z	1/h	apparent terminal elimination rate constant
λ_z Upper	h	end of exponential fit
λ_z Lower	h	start of exponential fit
λ_z N	Not applicable	number of data points included in the log-linear regression
λ_z Span Ratio	Not applicable	time period over which λ_z was determined as a ratio of $t_{1/2}$
R^2 -adj	Not applicable	adjusted coefficient for determination of exponential fit

Where possible, the span of time used in the determination of λ_z (ie the difference between λ_z Upper and λ_z Lower) should be ≥ 2 half-lives. If the λ_z Span Ratio is < 2 , the robustness of the $t_{1/2}$ values will be discussed in the CSR.

8.5.1.2. Criteria for Calculation and Reporting of Area Under the Concentration-time Curve

The minimum requirement for the calculation of AUC will be the inclusion of at least 3 consecutive concentrations above the lower limit of quantification. If there are only 3 consecutive concentrations, at least 1 should follow C_{max} .

If the extrapolated area is >20%, AUC_{0-inf} (and derived parameters) may be excluded from summary statistics and statistical analysis at the discretion of the sponsor or PK analyst.

If AUC_{0-inf} cannot be determined reliably for all subjects and/or dose levels/treatments, an alternative AUC measure, such as AUC to a fixed timepoint or AUC_{last} , may be used in the statistical analysis.

8.5.1.3. Calculation of Urinary Parameters

The amount of drug excreted in urine (A_e) and urine collection interval (t_1-t_2) will be calculated as the product of urine analyte concentration and urine volume. Where only urine sample weight is supplied, a specific gravity of 1 g/mL will be assumed, and it will be considered equivalent to urine volume. A total cumulative $A_{e0-x h}$ will be calculated by summing the $A_{e_{t_1-t_2}}$ values over the 0-x h interval, where x = end of the last collection time interval.

The percentage of the dose administered over the time interval t_1 to t_2 ($Fe_{t_1-t_2}$) as EIDD-2801 will be calculated for each urine collection interval as:

$$Fe_{t_1-t_2} = (A_{e_{t_1-t_2}} / \text{Dose}) \times 100\%.$$

The $Fe_{t_1-t_2}$ excreted as EIDD-1931 will be calculated for each urine collection interval as:

$$Fe_{t_1-t_2} = A_{e_{t_1-t_2, EIDD-1931}} / (\text{Dose}_{EIDD-2801} \times [MW_{EIDD-1931} / MW_{EIDD-2801}]) \times 100\%$$

Cumulative $Fe_{0-x h}$ will be calculated by summing the $Fe_{t_1-t_2}$ values over the 0-x h period in the same manner as $A_{e0-x h}$.

Renal clearance will be calculated as follows:

$$CL_R = A_e / AUC$$

where both A_e and AUC are determined over co-incident time ranges after dosing.

8.5.1.4. Criteria for Handling Below the Limit of Quantification or Missing Concentrations for Pharmacokinetic Analysis

Plasma concentration values that are below the limit of quantification (BLQ) will be set to a value of zero, with the following defined exceptions which will be set to missing:

- Any embedded BLQ value (between 2 quantifiable concentrations).
- BLQ values following the last quantifiable concentration in a profile.

- If an entire concentration-time profile is BLQ, it will be excluded from PK analysis.

Where 2 or more consecutive concentrations are BLQ at the end of a profile, the profile will be deemed to have terminated and any further quantifiable concentrations will be set to missing for the calculation of the PK parameters unless they are considered to be a true characteristic of the profile of the drug.

If a predose plasma concentration is missing, it may be set to zero by default.

Urine concentrations that are BLQ will be set to zero for the calculation of $Ae_{t_1-t_2}$.

8.5.1.5. Treatment of Outliers in Pharmacokinetic Analysis

If a value is considered to be anomalous due to being inconsistent with the expected PK profile, it may be appropriate to exclude this point from the PK analysis. However, the exclusion of data must have strong justification and will be documented in CSR.

Quantifiable predose concentration values prior to the first dose will be considered anomalous and set to missing for the PK analysis.

8.5.2. Presentation of Pharmacokinetic Data

If the actual time of sample collection deviates from the nominal time by more than $\pm 10\%$, the concentration will be flagged and excluded from summary statistics.

Individual concentrations that are deemed to be anomalous will be flagged in the listings and excluded from the summary statistics.

For PK concentration data, C_{max} and C_{trough} the following rules will be applied:

- Values that are BLQ will be set to 0 for calculation of summary statistics.
- Arithmetic mean or median that are BLQ will be presented as 0.

For PK parameters the following rule will be applied:

- Geometric mean and coefficient of variation will not be calculated for t_{max} , and t_{last} .

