7.3. Pharmacokinetic Population

The PK population will include all subjects receiving study drug who comply sufficiently with protocol requirements (i.e., no major protocol violations) and for whom a sufficient number of analyzable PK samples (at least 1 quantifiable postdose sample) have been obtained to permit the determination of the PK profile for EIDD-2801/EIDD-1931 and the statistical analysis of the results. Subjects who experience an AE of vomiting before $2 \times$ the median t_{max} of the group may be excluded from the PK population.

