8.5. Pharmacokinetic Assessments

8.5.1. Pharmacokinetic Analysis

PK parameters will be determined using non-compartmental methods in validated software program, Phoenix WinNonlin (Certara, Version 8.1 or higher).

The following parameters will be calculated where possible from the plasma concentrations of EIDD-2801 and EIDD-1931:

Parameter	Units ^a	Definition
AUC _{last}	h*ng/mL	the area under the plasma concentration-time curve, from time 0 to the last measurable non-zero concentration ^b , (Part 1, Part 2 and Part 3).
AUC _{0-inf}	h*ng/mL	the area under the plasma concentration-time curve from time 0 extrapolated to infinity ^{b,c} . (Part 1, Part 2, and Day 1 dose of Part 3).
AUC _τ	h*ng/mL	area under the plasma concentration-time curve during a dosing interval ^b (Part 3 only)
%AUC _{extrap}	%	percentage of AUC _{0-inf} that is due to extrapolation from the last quantifiable concentration to infinity

$\%AUC_{\tau, \text{extrap}}$	%	percentage of AUC_{τ} that is due to extrapolation from the last quantifiable concentration to the end of the dosing interval
C_{max}	ng/mL	maximum observed concentration
t_{max}	h	time of the maximum observed concentration
t_{last}	h	time of the last quantifiable concentration
λ_z	1/h	apparent terminal elimination rate constant
$t_{1/2}$	h	apparent terminal elimination half-life
CL/F	L/h	apparent clearance following an extravascular dose (EIDD-2801 only)
V_z/F	L	apparent volume of distribution during the terminal phase following and extravascular dose (EIDD-2801 only)
C_{trough}	ng/mL	plasma concentration at the end of the dosing interval (Part 3 only)
MR_{AUC}		EIDD-1931:EIDD-2801 ratio based on $AUC_{0-\text{inf}}$ (Day 1) or AUC_{τ} (Part 3 only, Day 6)
$MR_{C_{\text{max}}}$		EIDD-1931:EIDD-2801 ratio based on C_{max}
$RA_{AUC_{\tau}}$		observed accumulation ratio based on AUC_{τ} (Part 3 only).
$RA_{C_{\text{max}}}$		observed accumulation ratio based on C_{max} (Part 3 only).

^a Units are based on concentration units (provided by bioanalytical lab) and dose units used in the study.

^b AUC will be calculated using the linear trapezoidal rule for increasing concentrations and the logarithmic rule for decreasing concentrations (linear up/log down rule).

^c Based on last observed quantifiable concentration

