8.5.3.1. Dose Proportionality

In Part 1 on day 1 a statistical analysis will be conducted to investigate the dose proportionality of the [REDACTED] formulation for PK parameters of EIDD-2801 and EIDD-1931 (AUC_{0-inf} , AUC_{last} , and C_{max}).

A statistical analysis will also be conducted to investigate the dose proportionality of the [REDACTED] formulation on day 1 for PK parameters of EIDD-2801 and EIDD-1931 (AUC_{0-inf} , AUC_{last} , and C_{max}) by combining the day 1 Part 3 data with the Part 1 [REDACTED] cohorts.

In Part 3 on day 6 a statistical analysis will be conducted to investigate the dose proportionality for PK parameters of EIDD-2801 and EIDD-1931 (AUC_{τ} , and C_{max}). The dose proportionality assessments will include dose levels from a common dietary state.

The PK parameters will be analyzed using a power model³ that will have the following form:

$$parameter = intercept \times dose^{slope} + random\ error$$

Using the natural log (ln) transformation,⁴ a power model can be expressed as a linear regression equation:

$$\ln(parameter) = intercept + slope \times \ln(dose) + random\ error$$

For dose proportionality, the slope of the regression line is equal to 1; for dose independence, it is equal to 0.

For each PK parameter separately, a pooled estimate (across all doses) of slope, corresponding 90% confidence interval (CI), and between-subject coefficient of variation (CV) will be calculated. Figures (on the logarithmic scale) containing individual values, power model line (90% CI), and dose proportionality line (defined as the power model line with slope of 1) will be created for each PK parameter; figures (on the semi-logarithmic scale) containing individual values and geometric means will be created for each corresponding PK parameter normalized by dose administered.

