10. SIGNIFICANT CHANGES FROM THE PROTOCOL-SPECIFIED ANALYSES

EIDD-2801 concentration data were not quantifiable in some treatment groups and therefore PK parameters were not calculable. These affected groups will not have any parameter data presented and any analysis based upon these parameters will not be performed. Where limited samples were quantifiable (i.e. not a minimum of 3 consecutive concentrations with at least one after C_{max}) C_{max} and t_{max} may be reported.

The protocol indicated that the DMID toxicity grading scale would be used to grade laboratory parameters after taking into consideration institutional normal parameter ranges. The decision was made to evaluate out of reference laboratory parameters in the CSR only rather than using the DMID grading, as for several parameters the reference ranges used at the site were not consistent with the toxicity grading table provided in the protocol. Therefore, treatment-emergent toxicities based on DMID grading will not be reported and shift tables will be reported instead.

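### A BLQ Cmax for EIDD-2801 counts as 0 in one section and is excluded in another; neither fits the planned geometric means, and a partly BLQ low-dose group would bias the Cmax proportionality slope low

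*SAP*

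**What the plan says.** Section 8.5.2 covers concentrations, Cmax and Ctrough with one rule: "Values that are BLQ will be set to 0 for calculation of summary statistics". It explains how to show an arithmetic mean or median that is itself BLQ. For PK parameters it adds "Geometric mean and coefficient of variation will not be calculated for" tmax and tlast only, so a geometric mean remains planned for Cmax and Ctrough.

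Section 8.5.1.4, on BLQ values in the PK analysis, says: "If an entire concentration-time profile is BLQ, it will be excluded from PK analysis".

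Section 8.5.3.1 tests dose proportionality of Cmax on the ln scale ("a power model can be expressed as a linear regression equation"). Proportionality is concluded if linearity is acceptable and the 90% CI for the slope includes 1. If it is not concluded, an ANOVA of ln dose-normalised values compares the doses.

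Section 10 reports: "EIDD-2801 concentration data were not quantifiable in some treatment groups and therefore PK parameters were not calculable". It withdraws the parameters and analyses of the affected groups, and allows Cmax and tmax to be reported where only a few samples are quantifiable.

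**The concern.** Cmax is BLQ only when every sample in the profile is BLQ. Such a subject has Cmax = 0 under Section 8.5.2 and no Cmax under Section 8.5.1.4. The n, mean and median in the Cmax table depend on which section the programmer follows.

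The geometric mean has no workable rule: with one zero, the product form gives 0 and the log form is undefined.

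In the ln-scale models, ln(0) is missing and an excluded profile is absent, so either way the subject drops out. If only some subjects in a low-dose group are BLQ, those who stay are the high ones. That lifts the low end of the regression line and flattens the slope. The proportionality decision rests on whether the interval for that slope includes 1, so the selection bears directly on a stated conclusion.

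**Working it through.** The SAP gives no LLOQ, CV or BLQ rate and no power calculation, so there is no figure of its own to reproduce.

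**Inputs from the SAP.** Six active subjects per cohort (Section 5). Named doses are 50, 100, 200, 400, 600 and 800 mg in Part 1 (Section 6.1) and 50, 100, 200, 300 and 400 mg BID in Part 3 (Section 6.3). The model is ln(Cmax) on ln(dose) with a 90% CI (Section 8.5.3.1).

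**Assumptions.** True slope 1; log-normal Cmax with between-subject CV 40% or 60%; an LLOQ that makes one-sixth or one-half of 50 mg subjects BLQ; all doses of a Part in one model; BLQ subjects absent from the fit.

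**Step 1, ln-scale SD.** σ = √ln(1 + CV²), which is √ln 1.16 = 0.385 and √ln 1.36 = 0.555.

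**Step 2, shift in a half-BLQ group.** The mean of the upper half of a normal distribution exceeds the true mean by σ√(2/π) = 0.798σ. That is 0.307 (CV 40%) or 0.442 (CV 60%). The geometric mean of the quantifiable subjects alone is e^0.307 = 1.36 or e^0.442 = 1.56 times the truth.

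**Step 3, approximate slope.** Take x = ln(dose/50), with 3 subjects left at 50 mg and 6 at each other dose. The mean of x is 56.50/33 = 1.712, and the sum of squares about it is 26.80. Shifting only the 50 mg group changes the slope by −3 × 1.712 × shift / 26.80. This is −0.059 (slope 0.94) at CV 40% and −0.085 (slope 0.915) at CV 60%. At CV 60% about 11% of 100 mg subjects also fall below the same LLOQ, which lowers the slope further.

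**Step 4, simulation** (10,000 trials per setting, least squares, t-based 90% CI, Part 1 doses):

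| BLQ at 50 mg | CV | Mean slope | CI contains 1 | CI wholly below 1 |
|---|---|---|---|---|
| None | 40% / 60% | 1.00 / 1.00 | 90% / 91% | 5% / 5% |
| One-sixth | 40% / 60% | 0.97 / 0.95 | 89% / 88% | 10% / 10% |
| One-half | 40% / 60% | 0.94 / 0.89 | about 80% / 74% | 20% / 26% |
| 50 mg group dropped whole | 40% / 60% | 1.00 / 1.00 | 90% / 90% | – |

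Over the narrower Part 3 range with half of 50 mg BLQ, the slope is about 0.89 / 0.83 and coverage 76% / 71%.

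**Step 5, remedy.** A left-censored normal likelihood on the ln scale lets quantifiable subjects contribute their density and BLQ subjects Φ((ln LLOQ − mean)/σ). In the Part 1 settings it gave mean slopes of 1.00 to 1.01 (1,000 trials each).

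**The case against.** The strongest reply is that Sections 8.5.1.4 and 8.5.2 serve different purposes, one for deriving parameters and the other for displaying summaries. A subject could have no derived parameters and still show a Cmax of 0. That reading is possible and weakens the charge of contradiction. The SAP does not state it, though, and it leaves the geometric mean containing a zero.

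Second, Section 10 shows that whole groups were unquantifiable and removes them, which Step 4 shows is harmless. It does not say that any group was partly BLQ. This stands: partial quantifiability is an inference, and every slope figure is conditional on it. Section 10 also lets a Cmax be reported from few quantifiable samples, so only wholly BLQ subjects are lost from the Cmax models.

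Third, the SAP analyses formulations separately, so a single 50 to 800 mg regression is not its exact model. The figures are illustrative. A narrower range makes the bias larger, as Part 3 shows.

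Fourth, PK is a secondary objective in Parts 1 and 3, Section 8.1 cautions about interpreting the statistical results, and all concentrations will be listed. This limits the stakes without supplying a rule.

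A reader might go further than the document supports:

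- **All dose slopes are biased low.** This does not follow. AUClast runs "from time 0 to the last measurable non-zero concentration", so low-dose profiles are cut off sooner. Under assumed one-compartment profiles its slope was mostly biased upward (1.04 to 1.38). Ctrough is in no dose model.
- **Reported low-dose geometric means will be overstated.** Under the written rule they are 0 or undefined. The 1.36 to 1.56 factor applies only if zeros are dropped from the summaries, or to the least squares means of the ANOVA, which zeros cannot enter.
- **The fed/fasted comparison is affected.** Section 6.2 lists Part 2 at 200 mg, and nothing in the SAP indicates BLQ Cmax values there.

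**Conclusion.** The point holds in a limited form. The SAP does not settle whether an all-BLQ EIDD-2801 Cmax is 0 or absent, and it plans geometric means that its own zero rule makes unusable. It also fits Cmax on the ln scale with no provision for partly BLQ groups, in a trial where it already reports unquantifiable EIDD-2801 groups.

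If a modelled low-dose group is partly BLQ, the EIDD-2801 Cmax slope is biased low and the interval rule for proportionality is miscalibrated. The bias is small with one-sixth BLQ (slope 0.95 to 0.97, coverage about 88 to 89%) and material with half BLQ (0.89 to 0.94, about 74 to 80%). These sizes rest on the assumed LLOQ, CV, BLQ rates and single pooled model. The point does not extend to the AUC models, to any model of Ctrough, or to the food-effect analysis. It should be corrected, but it does not threaten the primary safety objectives.

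**What to change.** 1. State one rule for an all-BLQ Cmax and use it in both Sections 8.5.1.4 and 8.5.2.
2. Where any Cmax or Ctrough in a group is BLQ, report the number BLQ, the median and the range, and no geometric mean.
3. Where any dose group in an EIDD-2801 Cmax proportionality model is partly BLQ, fit a left-censored ln-normal power model with all-BLQ subjects censored at the LLOQ, at least as a sensitivity analysis. Qualify the proportionality conclusion if the two fits disagree.

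The cost is a few lines of SAP text, one more column in the tables and one extra censored-regression run. The censored fit relies on the log-normal shape below the LLOQ, which the data cannot check.

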8.5.3. Pharmacokinetic Statistical Methodology

All PK concentrations and parameters will be listed.

Summary tables, mean figures, overlaying individual figures, and individual figures by treatment and time postdose will be provided for plasma PK concentrations. All figures will be produced on both linear and semi-logarithmic scales.

Summary tables by treatment will be provided for all plasma PK parameters, with the exception of diagnostic regression-related PK parameters. Separate summary tables by treatment and time interval will be provided for urine PK parameters.

8.5.3.1. Dose Proportionality

In Part 1 on day 1 a statistical analysis will be conducted to investigate the dose proportionality of the [REDACTED] formulation for PK parameters of EIDD-2801 and EIDD-1931 (AUC_{0-inf} , AUC_{last} , and C_{max}).

A statistical analysis will also be conducted to investigate the dose proportionality of the [REDACTED] formulation on day 1 for PK parameters of EIDD-2801 and EIDD-1931 (AUC_{0-inf} , AUC_{last} , and C_{max}) by combining the day 1 Part 3 data with the Part 1 [REDACTED] cohorts.

In Part 3 on day 6 a statistical analysis will be conducted to investigate the dose proportionality for PK parameters of EIDD-2801 and EIDD-1931 (AUC_{τ} , and C_{max}). The dose proportionality assessments will include dose levels from a common dietary state.

The PK parameters will be analyzed using a power model³ that will have the following form:

$$parameter = intercept \times dose^{slope} + random\ error$$

Using the natural log (ln) transformation,⁴ a power model can be expressed as a linear regression equation:

$$\ln(parameter) = intercept + slope \times \ln(dose) + random\ error$$

For dose proportionality, the slope of the regression line is equal to 1; for dose independence, it is equal to 0.

For each PK parameter separately, a pooled estimate (across all doses) of slope, corresponding 90% confidence interval (CI), and between-subject coefficient of variation (CV) will be calculated. Figures (on the logarithmic scale) containing individual values, power model line (90% CI), and dose proportionality line (defined as the power model line with slope of 1) will be created for each PK parameter; figures (on the semi-logarithmic scale) containing individual values and geometric means will be created for each corresponding PK parameter normalized by dose administered.

The lack of fit test will be conducted for the statistical assessment of linearity assumption, and thus appropriateness of a power model. The lack of fit model will be the same as the power model fitted, but with dose included as additional fixed effect. The statistical assessment will rule the linearity assumption acceptable if the diagnostic plots appear reasonable and the lack of fit p-value >0.05 (dose effect is not significant at the 0.05 level of significance). The assessment of linearity assumption may also occur via visual examination of the figures by the pharmacokineticist. This assessment may override the statistical assessment; where this occurs, it will be detailed in the CSR.

It will be concluded that PK parameter is dose proportional for the dose range studied if the assumption of linearity is ruled acceptable and the 90% CI for the slope spans 1.

In the case of lack of dose proportionality, between treatment pairwise comparisons based on ln-transformed dose normalized PK parameters will be performed using an analysis of variance (ANOVA) model.⁵ The model will include dose as a factor. For each PK parameter separately, the least squares mean (LSM) for each dose, difference in LSMs between each

dose, and corresponding 90% CIs will be calculated; these values will then be back-transformed to give the GLSM, ratio of GLSMs, and corresponding 90% CI.

Examples of the SAS code that will be used are as follows:

Power Model Analysis

```
proc mixed data = <data in> alpha = 0.1;
  by parcat1n parcat1 pkday paramn param;
  model lpk = ldose / cl residual ddfm = kr2;
  ods output solutionf = <data out>;
run;
```

Power Model Analysis (Between-subject Variability)

```
proc mixed data = <data in> covtest alpha = 0.05;
  by parcat1n parcat1 pkday paramn param;
  class ldose;
  model lpk = ldose / cl residual ddfm = kr2;
  ods output covparms = <data out>;
run;
```

(Note: Pooled Geometric CV (%) = $100 * (\text{sqrt}(\text{exp}(\text{estimate}) - 1))$)

Power Model Analysis (Lack of Fit Test)

```
proc mixed data = <data in>;
  by parcat1n parcat1 pkday paramn param;
  class dose;
  model lpk = ldose dose / htype = 1 ddfm = kr2;
  ods output tests1 = <data out>;
run;
```

ANOVA Model Analysis

```
proc mixed data = <data in> alpha = 0.1;
  by parcat1n parcat1 pkday paramn param;
  class dose;
  model ldnpk = dose / cl residual ddfm = kr2;
  lsmeans dose / cl pdiff alpha=0.1;
  ods output lsmeans = <data out>;
  ods output diffs = <data out>;
  ods output tests3 = <data out>;
run;
```

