4.1.1. Part 1 (Single Ascending Dose)

A single oral dose of EIDD-2801 or Placebo will be administered to subjects. Subjects will be randomized in a 3:1 ratio to receive either EIDD-2801 or Placebo.

Following dosing on Day 1, subjects will remain in the clinic through completion of study assessments on Day 4, returning to the clinic on Day 9 for study assessments, and Day 15 for the end of study (EOS) visit.

The first cohort will be divided into 2 groups. The first group, a sentinel group, will include 2 subjects. On Day 1, one subject in the sentinel group will be administered Placebo and one will be administered EIDD-2801. Analysis of the safety results for the sentinel group will be reviewed 24 hours postdose. If no halting criteria have been met, the remainder of the subjects in Cohort 1 (the second group) will be dosed. There will be no sentinel groups for the remaining cohorts.

After completion of each dosing cohort, safety and tolerability data will be reviewed to determine if any of the halting rules have been met. If not, then the subsequent cohort may be dosed following review of the 72-hour safety data. As PK data become available, these data may be used for dose-escalation decisions.

The proposed dose-escalation scheme is shown in

Figure 1, however, planned dose escalations will be determined based on ongoing review of the safety, tolerability, and available PK data. The starting dose in the first SAD cohort will be 50 mg. Dose levels will not increase by more than 3-fold for predicted nonpharmacologically active dose levels and by 2-fold for predicted pharmacologically active dose levels. The highest total daily dose to be studied under this protocol will not exceed 1600 mg.

Three cohorts are initially planned for Part 1; however, up to an additional 7 cohorts may be enrolled.

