4.1.3. Part 3 (Multiple Ascending Dose)

Subjects in Part 3 will be randomized in a 3:1 ratio to receive either EIDD-2801 or Placebo. Twice-daily dosing will be administered to subjects on Day 1 through Day 5, inclusive, and a final dose will be administered on the morning of Day 6 for collection of steady-state PK samples during waking hours. Depending on ongoing review of the safety, tolerability, and PK data, the number of days of dosing may be reduced and the dosing frequency may be changed; the dosing frequency will be no less than once-daily or no greater than three-times daily.

The proposed dose-escalation scheme is shown in

Figure 1. The total daily dose will not exceed a dose shown to be safe and well-tolerated in Part 1. Doses in Part 3 may be administered in the fed state, following review of the PK data obtained from Part 2. Part 3 may run in parallel with Part 1, providing that the total daily dose to be administered does not exceed a dose already shown to be safe and well-tolerated in Part 1.

[figure not shown]
Subjects will remain domiciled at the site during the dosing period and until Day 9, returning to the clinic on Day 14 for completion of study assessments, and Day 20 for the EOS visit. If the number of days of dosing are reduced, the timepoints for subsequent assessments and the period for which subjects are domiciled at the clinic will similarly be changed (subjects will be domiciled for 3 days post final dose).

Three cohorts are initially planned for Part 3; however, up to an additional 6 cohorts may be enrolled, or the number of cohorts may be reduced if the study objectives are met. Dose levels in Part 3 may be repeated for collection of peripheral blood mononuclear cells (PBMCs), providing that the dose level did not meet the dose-escalation halting criteria.

[figure not shown]
Additional parts may be added to this study, including a SAD part in elderly healthy subjects and a study of the safety, tolerability, and PK in Japanese subjects. These additional parts may be added via a protocol amendment.

Figure 1: Study Design

[figure not shown]
PART 1: SAD Cohorts

PART 2: Food Effect (FE) Cohort

PART 3: MAD Cohorts**

Abbreviations:

FE: food effect

SAD: single ascending dose

MAD: multiple ascending dose

** Part 3 may run in parallel with Part 1, providing that the total daily dose to be administered does not exceed a dose already shown to be safe and well tolerated in Part 1

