6. STUDY TREATMENTS

All treatments described are the planned treatments. The TFLs will reflect the actual treatments received, and dose levels will be displayed in increasing order where applicable. Screen failure subjects will have treatment ‘Screen Failure’ presented in all applicable listings.

6.1. Part 1

The study treatment names, abbreviations, and ordering to be used in the TFLs are presented in [Table 1](#).

Table 1: Presentation of Study Treatments in TFLs

Study Treatment	Order in TFLs
Placebo (fasted)	1
50 mg EIDD-2801 [REDACTED] (fasted)	2
100 mg EIDD-2801 [REDACTED] (fasted)	3
200 mg EIDD-2801 [REDACTED] (fasted)	4
400 mg EIDD-2801 [REDACTED] (fasted)	5
600 mg EIDD-2801 [REDACTED] (fasted)	6
800 mg EIDD-2801 [REDACTED] (fasted)	7
XXX mg EIDD-2801 [REDACTED] (fasted)	8

Additional treatment labels may be added in the same format if additional cohorts are required. Amend the formulation as required as changes may occur throughout the study. All Placebo groups will be pooled [REDACTED] for summaries but in the listings the formulation will be indicated in the treatment label as ‘Placebo [REDACTED] (fasted)’ or ‘Placebo [REDACTED] (fasted)’.

As the capsule formulation is expected to be utilized for the latter cohorts, the [REDACTED] EIDD-2801 treatment groups will be summarized after the [REDACTED] EIDD-2801 treatment groups.

6.2. Part 2

The study treatment names, abbreviations, and ordering to be used in the TFLs are presented in [Table 2](#).

Table 2: Presentation of Study Treatments in TFLs

Study Treatment	Order in TFLs
200 mg EIDD-2801 [REDACTED] (fasted)	1
200 mg EIDD-2801 [REDACTED] (fed)	2

Additional treatment labels may be added in the same format if additional cohorts are required. Amend the formulation as required as changes may occur throughout the study.

The study treatment sequence names, abbreviations, and ordering to be used in the TFLs are presented in [Table 3](#).

Table 3: Presentation of Study Treatment Sequences in TFLs

Study Treatment Sequence	Abbreviation	Order in TFLs
200 mg EIDD-2801 ██████ (fed) / 200 mg EIDD-2801 ██████ (fasted)	200 mg EIDD-2801 ██████ (fed/fast)	1
200 mg EIDD-2801 ██████ (fasted) / 200 mg EIDD-2801 ██████ (fed)	200 mg EIDD-2801 ██████ (fasted/fed)	2

Additional treatment sequences may be added in the same format if an additional cohort at a different dose level is required. Amend the formulation as required as changes may occur throughout the study.

6.3. Part 3

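### The pooled Part 1 and Part 3 Day 1 dose-proportionality analysis compares AUC_last over unequal windows that probably track dose, so the AUC_last slope is expected to be biased upward unless little is quantifiable after the Part 3 dosing interval

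*SAP*

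**What the plan says.** SAP Section 8.5.3.1 first plans a Part 1 analysis of one formulation. It then adds a second: "A statistical analysis will also be conducted to investigate the dose proportionality of the" other formulation (name redacted), "by combining the day 1 Part 3 data with the Part 1" cohorts that used it. The pooled parameters are AUC_0-inf, AUC_last and C_max, for both analytes.

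The two sources differ in design:

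- **Part 3 (Section 4.1.3):** "Twice-daily dosing will be administered to subjects on Day 1 through Day 5, inclusive". The frequency may change to anything from once to three times daily.
- **Part 1 (Section 4.1.1):** one dose only, after which "subjects will remain in the clinic through completion of study assessments on Day 4".

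Section 8.5.1 defines AUC_last as the area "from time 0 to the last measurable non-zero concentration", for all three Parts. AUC_tau, the area "area under the plasma concentration-time curve during a dosing interval", is for Part 3 only. AUC_0-inf is defined for Parts 1 and 2 and for the Part 3 Day 1 dose.

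The power model regresses ln(parameter) on ln(dose) and nothing else. Proportionality is concluded if linearity is accepted and the 90% CI for the slope contains 1.

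**The concern.** AUC_last depends on how long a profile can be followed. A Part 3 Day 1 value cannot extend past the second dose and still describe a single dose, whereas a Part 1 value has no such limit. If appreciable drug remains after the dosing interval, the Part 3 values are smaller at the same true exposure.

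This would be only noise if the windows were spread evenly over dose, but they probably are not:

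- Section 6.1 says "As the capsule formulation is expected to be utilized for the latter cohorts", and the Part 1 design escalates. The document history ties the pooled analysis to the formulation used in those later cohorts.
- Section 4.1.3 caps the Part 3 total daily dose at one already tolerated in Part 1, so under twice-daily dosing the unit dose is at most half of that.
- Table 4 lists 50 to 400 mg for Part 3, while Table 1 reaches 800 mg for Part 1. Both have open rows.

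Short windows therefore tend to fall at low doses and long ones at high doses. Without a Part term, the slope absorbs the difference. A proportional drug may look more than proportional, and a less-than-proportional one may look proportional.

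**Working it through.** The SAP gives no half-life, CV or slope precision, so there is no figure of its own to reproduce. The check asks how far the AUC_last slope moves when the truth is exact proportionality.

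**Inputs from the SAP:** 6 active subjects per cohort (Section 5); ln(dose) as the only covariate; 90% CI decision rule.

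**Assumptions:** Part 3 at 50, 100, 200, 300 and 400 mg; Part 1 cohorts of this formulation at 600 and 800 mg; a 12 h interval; CV 30% (20% as a variant). A fraction f of the Part 1 AUC_last lies after 12 h and is missing in Part 3.

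**Step 1, bias.** With x = ln(dose) and n = 42, mean x = 5.513 and Sxx = 35.12. The 12 Part 1 subjects have mean x = 6.541. A Part 1 shift of −ln(1−f) moves the least-squares slope by

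bias = −ln(1−f) × 12 × (6.541 − 5.513) / 35.12 = −ln(1−f) × 0.351.

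For f = 10%, this is 0.1054 × 0.351 = 0.037.

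**Step 2, precision.** The SD on the log scale is √ln(1 + 0.30²) = 0.294. The SE is 0.294/√35.12 = 0.0495. With t(0.95, 40 df) = 1.684, the 90% CI half-width is 0.083. At CV 20% it is 0.056.

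**Step 3, chance that the CI wrongly excludes 1.** Noncentral t, 40 df, noncentrality bias/SE.

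| Part 1 AUC after 12 h | Slope bias | Excludes 1, CV 30% | Excludes 1, CV 20% |
|---|---|---|---|
| 0% | 0 | 10% | 10% |
| 2% | +0.007 | 10% | 11% |
| 5% | +0.018 | 12% | 15% |
| 10% | +0.037 | 19% | 29% |
| 15% | +0.057 | 31% | 51% |
| 20% | +0.078 | 46% | 75% |

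**Step 4, which f to expect.** For a one-compartment oral profile with absorption rate 2/h (assumed) and elimination rate k, the fraction after 12 h is [2·exp(−12k) − k·exp(−24)]/(2 − k). It is about 0.04% at a half-life of 1 h, 1.9% at 2 h, 14% at 4 h and 37% at 8 h. With Part 1 followed to 72 h, the slopes are 1.000, 1.007, 1.052 and 1.161. At 4 h, the slope is 1.112 under three-times-daily dosing and 1.006 under once-daily dosing.

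**Step 5, other dose sets.** With overlapping doses (Part 3 at 50, 100, 200, 300, 400, 600 and 800 mg; Part 1 at 400, 600 and 800 mg), the multiplier falls from 0.351 to 0.234. The bias is then 0.012 to 0.052 for f of 5 to 20%. If the pooled Part 1 cohorts were the lowest doses, the bias would be downward (slope 0.803 at an 8 h half-life).

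**Step 6, the lack-of-fit test.** The artefact nearly follows ln(dose), so the test seldom sees it. In the base case at CV 30%, its power is about 6, 7, 11 and 16% for f of 5, 10, 15 and 20%, against a nominal 5%.

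**Step 7, the other pooled parameters.** C_max does not depend on the window once the peak has passed. AUC_0-inf has no bias with a single log-linear phase. With an assumed slow second phase (5 to 20% of AUC, half-life 7 to 20 h) unseen in Part 3, its slope is 1.004 to 1.041.

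**Step 8, common window.** With the same window in both Parts, the slope is 1.000 at every half-life tested (1, 4, 8 and 24 h).

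**The case against.** A reader might infer that every pooled AUC is compared over unequal windows. The SAP does not support that. AUC_0-inf is extrapolated and so has no window by definition. Section 8.5.1.1 requires at least 3 points and an adjusted R² of at least 0.7 for the terminal slope, and Section 8.5.1.2 allows exclusion when more than 20% is extrapolated. What remains is indirect: a poorly observed terminal phase, and an exclusion rule left to discretion.

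A reader might also take the upward bias as established. It is conditional. The SAP gives neither half-life nor assay limit, and at a 2% tail the effect is negligible. The Day 4 stay is for study assessments, and PK sampling times are not in the SAP. Formulation by dose is redacted, so 600 and 800 mg are assumptions. The confounding with dose is well supported but not proven.

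Section 8.5.1.2 already permits AUC to a fixed timepoint. However, this is optional, is triggered only by unreliable AUC_0-inf, and names AUC_last as an equal substitute.

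Section 10 says that EIDD-2801 was not quantifiable in some groups and that dependent analyses will be dropped, so the point may bear mainly on EIDD-1931. Section 8.1 urges caution because the study is not powered, and t_last is listed, so a careful reader could notice the difference. All of this lowers the severity. None of it makes the AUC_last values comparable.

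**Conclusion.** The point holds for AUC_last in the combined analysis. The plan pools a profile that ends by the next dose with one that may run much longer, sets no common window and has no Part term. The slope is expected to be biased upward unless concentrations are essentially unquantifiable by the end of the dosing interval. Under the assumed doses and CV 30%, the bias is trivial at a 2% tail. At a 20% tail it is nearly as large as the CI half-width (0.078 against 0.083). The direction rests on Part 3 holding the lower unit doses.

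Severity is moderate. PK is secondary in Parts 1 and 3, where the primary endpoints are safety, and a case for treating this as critical is not supported.

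**What to change.** In Section 8.5.3.1, for the combined analysis only:

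1. Replace AUC_last with a partial AUC from 0 to the actual Part 3 Day 1 dosing interval (0–12 h if twice daily), calculated the same way in both Parts. Tie it to the actual interval, since Section 4.1.3 allows the frequency to change. If pooled cohorts differ in frequency, use the shortest interval throughout.
2. Keep C_max.
3. Keep AUC_0-inf, with the exclusion for more than 20% extrapolation applied as a fixed rule rather than at discretion.

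A Part term is not an adequate substitute. If doses do not overlap between Parts, it can be separated from the dose effect only by relying on the assumed straight line.

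The cost is SAP wording and one partial AUC from samples already collected. The downside is that the pooled analysis no longer describes exposure beyond the dosing interval; Part 1 alone still does.
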